**1.7.3 Rationale for Expansion Cohort**

Based on initial portion of the study where the first 18 evaluable patients were investigated, a striking difference between overall response rates in ER-positive and TNBC was observed (Table 1). The ORR in ER-positive was 0%, and in TNBC it was 42.9%. Furthermore, the TNBC group had 2 patients with SD (clinical benefit rate of 71.4%), and one of the patients listed as PD, in fact had pseudoprogression (after 2 months had sub-centimeter LNs enlarge to >15mm, captured as PD per RECIST, but afterwards experience stability in these lesions, and a PR in target lesions). While the numbers are small, there is a clear signal in the TNBC cohort since essentially 6 out of 7 patient experienced clinically relevant benefit. Immunotherapy is rapidly evolving in breast cancer, and these initial results show promise in this cohort of patients, and the rationale of the expansion cohort is to capitalize on this initial experience.

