**NU Study Number: NU 15B01**

**Other Study Number: MedImmune # ESR-14-10694 (D4190C00030)**

**3.0 PATIENT ELIGIBILITY**

The target population for this study is patients with stage IV (metastatic) HER2 negative breast cancer (both male and female patients are eligible). This will be a single-center trial conducted at Northwestern University. The expansion cohort will only include metastatic TNBC.

Eighteen patients will be added in the first stage. If 4 or more respond, then an additional 10 patients will be added for a total of 28. A total of 30 subjects (15 ER+, 15 ER) will be needed to obtain a total of 28 evaluable patients (14ER+ and 14ER-) for this trial. The expansion cohort will include 20 evaluable patients with TNBC. Approximately 5 potentially eligible patients are seen per month, and it is anticipated that at least 2 per month will be accrued. Potential patients may be referred to the Principal Investigator (PI) at Northwestern University, [name] at [contact].

Eligibility will be evaluated by the study team according to the following criteria. Eligibility waivers are not permitted. Subjects must meet all of the inclusion and none of the exclusion criteria to be registered to the study. Study treatment may not begin until a subject is registered. Please refer to Section 11 for complete instructions regarding registration procedures.

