#### **10.2**

#### **Sample Size and Accrual**

A total of 35 patients (as needed) with metastatic breast cancer which is HER2 negative will be enrolled into this study and receive durvalumab in combination with tremelimumab, in order to get 28 evaluable for response. 15 patients with ER-positive disease and 15 patients with ER-negative disease will be enrolled (i.e. 2 cohorts with 14 evaluable each). Patients who have completed the week 8 CT or nuclear bone scan will be evaluable for response endpoints. Bone scans will be done only if the patient has bone disease. PET-CT is acceptable in place of bone scan, if a bone scan is contra-indicated for a patient's disease. The same modality used at baseline should be used throughout.

Using a Simon's two-stage design, we assume the undesirable overall response rate (null hypothesis) to be approximately 10%, and the alternate hypothesis to be approximately 30% based on previously published and presented data. Eleven patients will be added in the first stage. If 2 or more respond, then an additional 16 patients will be added for a total of 27. If 6 or more respond, then the hypothesis that the response rate is at least 30% is supported. This design has a Type I error rate of 4% and 80% power, and has a 70% chance of stopping early for futility after the first stage if the true response rate is 10%. The design is based on the complete sample and is not stratified by estrogen receptor status. ORR will also be calculated separately by receptor status, but the study is not powered for analyses within these subgroups.

For the expansion cohort we expect the ORR based on RECIST v1.1 to exceed 30% given our preliminary data. Using a Bayesian design assuming a prior beta distribution with parameters 0.3 and 0.7, there is a posterior probability of 0.81 that the ORR exceeds 30% if 8 or more responses out of 20 evaluable patients are observed.

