#### **10.3**

#### **Data Analyses Plans**

The primary analysis will be on the intent-to-treat (ITT) population, including all evaluable patients. Best ORR defined as will be defined as number (%) of patients with at least one visit response of complete or partial response by the Response Evaluation Criteria in Solid Tumors (RECIST 1.1). Best objective response prior to disease progression will be used. The overall response rate will be estimated by the proportion of overall response, and its 80% confidence interval (CI) and 95% CI will be estimated using the exact binomial distribution.

Additionally, we will evaluate clinical benefit rate, defined as stable disease for  $\geq 12$  weeks complete or partial response using RECIST 1.1 guidelines in a similar manner. We will also perform similar analyses using Immune Related RECIST (irRECIST).

PFS is defined as the time from date of treatment initiation until date of documented disease progression or death (by any cause in the absence of progression). OS is defined as the time from the date of start of treatment until death due to any cause. For patients alive at the time of data cut-off, PFS and OS will be censored as of the last tumor assessment date or known to be alive, respectively. The PFS and OS will be estimated using the Kaplan-Meier method. The number, frequency, and severity of adverse events (as defined by the NCI Common Terminology Criteria for Adverse Events or CTCAE version 4.03) will be recorded.

Baseline percent PDL1 expression, TILs (sTILs, iTILs, and their ratio), and changes in T cell subpopulations will be used as a continuous variable to predict clinical benefit or overall response rates using appropriate statistical summaries. Cox proportional hazards regression will be used to compare how these biomarkers are associated with PFS and OS as well.

Changes from baseline in these biomarkers will also be analyzed to assess for pharmacodynamic effects of treatment. Continuous variables will be analyzed using either paired t-tests, signed rank tests or repeated measures analysis of variance.

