Section 3.1.1 Inclusion criteria and Study summary	Criteria stated requirements for both general and expansion cohort. Expansion cohort included. The expansion cohort will only include HER2- negative, ER and PR- negative patients.	The general cohort details are now included as a note. The Expansion cohort will now enroll only metastatic TNBC patients.	Enrollment to general cohort is done. Only expansion cohort is now enrolling patients. TNBC patients alone are being enrolled. Rationale explained in section 1.7.3
Section 3.1.3 Inclusion criteria and Study summary	Along with other requirements, patients with ER positive disease were included.	Patients with ER positive disease removed and PD-L1 negative patients in the front line setting are now eligible. A note has been inserted to clarify that beyond frontline, any PD-L1 status is acceptable	Based on current clinical landscape, explained in the background section.
Section 3.2.6 Exclusion criteria	For ECGs the Friderica's Correction was listed	Friderica's correction replaced by Bazett's formula.	To align with standard procedures used at NU

Section 3.1.13 Inclusion criteria	Criteria regarding birth control	Inserted Appendix A	For clarity and consistency
Section 4.3 Toxicity Management & Dose Delays/Modifications	Previous version of toxicity management guidelines	Removed previous version. Inserted : Updated toxicity management guidelines (dated Oct 2019)	Based on information received from AstraZeneca
Section 4.9 Patient replacement	A patient who does not reach the first imaging assessment at 2 months for reasons other than clinical progression may be replaced. They will not be used toward assessment of the primary clinical endpoint (ORR), PFS or OS. However, they will be included in the final safety analysis	Previous language has been reworded to state:  “A patient who does not reach the first imaging assessment at 2 months for reasons other than clinical progression will not be used toward assessment of the primary clinical endpoint (ORR), PFS or OS. However, they will be included in the final safety analysis. Additional patients may be added if needed for assessment of response.”	For increased clarity

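### Section 10.2 reads 6 or more responders of 27 as support for a response rate of at least 30%, but the two-stage rule only rejects a rate of 10% or less

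*Combined protocol and SAP*

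**What the plan says.** Section 10.2 (Sample Size and Accrual) of the combined protocol and SAP gives the general cohort a Simon two-stage design. On the hypotheses it says "we assume the undesirable overall response rate (null hypothesis) to be approximately 10%, and the alternate hypothesis to be approximately 30" percent. Eleven patients enter stage one. Two or more responders lead to 16 further patients, 27 in all. The success rule is: "If 6 or more respond, then the hypothesis that the response rate is at least 30% is supported". The operating characteristics follow: "This design has a Type I error rate of 4% and 80% power", with a 70% chance of stopping after stage one if the true rate is 10%.

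Section 10.3 (Data Analyses Plans) adds that ORR will be estimated and that "its 80% confidence interval (CI) and 95% CI will be estimated using the exact binomial distribution". It states no other success criterion for the general cohort and no test of ORR against 30%.

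Section 3.0 describes a different rule, with 18 patients in stage one: "If 4 or more respond, then an additional 10 patients will be added for a total of 28". It gives no final cutoff and no error rates.

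**The concern.** A two-stage design of this kind controls the chance of declaring success when the true rate equals the null. Crossing the final boundary is therefore evidence against the null rate, here 10%. The alternative rate, 30%, only fixes the power. The sentence in section 10.2 moves the conclusion from the rate being tested to the rate used for power.

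Taken literally, it would let the trial report 6 responders of 27 as support for an ORR of at least 30%, when the observed rate is below 30% and the design offers no error control at that value. No other success conclusion is stated for the general cohort's primary endpoint, so nothing else in the plan corrects it.

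**Working it through.** **Inputs (section 10.2).** Null ORR 0.10; alternative 0.30; stage one n = 11, continue at 2 or more; stage two n = 16; total 27, success at 6 or more. The word one-sided is not used. It follows from a rule with an upper boundary only.

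**Step 1: reproduce the plan's own figures.**

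Early stopping at 10%: 0.9^11 + 11 × 0.1 × 0.9^10 = 0.3138 + 0.3835 = 0.697. The plan says 70%.

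Probability of success at true rate p:

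P(success) = Σ (x = 2 to 11) P(X₁ = x) × P(X₂ ≥ 6 − x), with X₁ ~ Bin(11, p) and X₂ ~ Bin(16, p).

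| Stage-one responders | p = 0.10 | p = 0.20 | p = 0.30 |
|---|---|---|---|
| 2 | 0.2131 × 0.0684 = 0.0146 | 0.2953 × 0.4019 = 0.1187 | 0.1998 × 0.7541 = 0.1506 |
| 3 | 0.0710 × 0.2108 = 0.0150 | 0.2215 × 0.6482 = 0.1435 | 0.2568 × 0.9006 = 0.2313 |
| 4 | 0.0158 × 0.4853 = 0.0077 | 0.1107 × 0.8593 = 0.0951 | 0.2201 × 0.9739 = 0.2144 |
| 5 | 0.0025 × 0.8147 = 0.0020 | 0.0388 × 0.9719 = 0.0377 | 0.1321 × 0.9967 = 0.1316 |
| 6 or more | 0.0003 | 0.0117 | 0.0782 |
| **Total** | **0.0395** | **0.407** | **0.806** |

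The stated 4% and 80% are reproduced. The 4% is the column at 10%; the 80% is the column at 30%. The 20% column is an assumed rate, not a figure from the plan.

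**Step 2: how often a rate below 30% crosses.** The same formula gives 0.180 at 15%, 0.407 at 20%, 0.636 at 25% and 0.778 at 29% (all assumed true rates). Some crossing below the alternative is normal for any such boundary. It becomes a problem only because the sentence attaches a claim about 30% to the crossing.

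**Step 3: what the data look like at the boundary.** Exact (Clopper-Pearson) intervals, as planned in section 10.3:

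| Responders of 27 | Observed ORR | Exact 80% CI | Exact 95% CI |
|---|---|---|---|
| 6 | 22.2% | 12.1% to 35.8% | 8.6% to 42.3% |
| 7 | 25.9% | 15.1% to 39.7% | 11.1% to 46.3% |
| 8 | 29.6% | 18.1% to 43.6% | 13.8% to 50.2% |

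All three counts are successes under the rule, and all three are observed rates below 30%. No lower limit is close to 30%.

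At exactly 6 of 27 the 95% interval also includes 10%. It places 2.5% in each tail, while the test uses about 4% in one tail. From 7 upwards the interval and the test agree about 10%. These intervals ignore the two-stage sampling.

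**Step 4: what a test against 30% would need.** For comparison, a single-stage exact one-sided 5% test of ORR of 30% or less with 27 patients needs 13 responders: P(X ≥ 13 | 27, 0.30) = 0.036, while P(X ≥ 12 | 27, 0.30) = 0.080. The plan's cutoff is 6.

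**The case against.** The strongest reply is that the sentence only names the design's own alternative. Section 10.2 labels 10% the null and 30% the alternative, and says supported, not demonstrated. Of those two point values, 6 of 27 is the first count to favour 30%. The likelihood ratio is 3^x × (7/9)^(27−x), which is 0.96 at 5 responders and 3.72 at 6. Both planned intervals at 6 of 27 contain 30%, so the result does not contradict that rate. On this reading the wording is loose but no analysis is wrong.

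Part of this stands: no boundary, sample size or computation depends on the sentence. But favouring 30% over 10% is a reason to reject 10%. It is not support for the composite statement that the rate is at least 30%, since 22.2%, the observed rate, fits better than 30%.

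The second reply is that little now turns on it, and this has real weight:

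- The Amendment 11 entry in Appendix E says of the general cohort "Enrollment to general cohort is done", and the Amendment 12 entry records that the study closed on 20 July 2020 for low accrual.
- Section 1.7.3 reports results "Based on initial portion of the study where the first 18 evaluable patients were investigated", with 3 responders of 18 (16.7%). That is below the threshold of 4 in section 3.0, so under that rule the final boundary would not be reached.

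However, 3 of 18 is not by itself below the continuation rule in section 10.2 (2 of 11). The documents do not give the final number of evaluable patients in the general cohort. If 27 were evaluated, the sentence governs the conclusion.

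**Conclusion.** The concern holds. The boundaries, type I error, power and early-stopping probability in section 10.2 are all correct; the conclusion attached to the final boundary is not. Reaching 6 of 27 rejects an ORR of 10% or less at a one-sided level of 0.0395. It does not support an ORR of at least 30%: the observed rate at the boundary is 22.2%, and a true ORR of 20%, if assumed, would cross 41% of the time.

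This should be fixed, but it is a correction to what the trial may claim, not to how it is run. Completed enrolment, study closure and the planned intervals limit the damage. The finding rests on the 11/27 rule in section 10.2 and on reading the test as one-sided.

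**What to change.** Replace the success sentence in section 10.2 with wording such as:

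> If 6 or more of 27 evaluable patients respond, the null hypothesis that ORR is 10% or less is rejected at a one-sided type I error of about 4%. The design has 80% power if the true ORR is 30%.

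Report ORR with the exact 80% and 95% intervals already planned in section 10.3. Add a short note that they are not adjusted for the two-stage design and that at exactly 6 of 27 the two-sided 95% interval still includes 10%. Make no claim of an ORR of at least 30% from crossing the boundary.

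This wording applies only to the rule in section 10.2. The 18/28 rule in section 3.0 must be reconciled with it separately. Because that rule has no stated final cutoff, its type I error at 10% could be 0.074, 0.039 or 0.015 for assumed cutoffs of 5, 6 or 7 of 28, and no conclusion can be attached to it as it stands.

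The cost is one sentence and one note. Sample size, boundaries, error rates and analyses are unchanged; the only loss is a more modest claim.

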#### **10.3**

#### **Data Analyses Plans**

The primary analysis will be on the intent-to-treat (ITT) population, including all evaluable patients. Best ORR defined as will be defined as number (%) of patients with at least one visit response of complete or partial response by the Response Evaluation Criteria in Solid Tumors (RECIST 1.1). Best objective response prior to disease progression will be used. The overall response rate will be estimated by the proportion of overall response, and its 80% confidence interval (CI) and 95% CI will be estimated using the exact binomial distribution.

Additionally, we will evaluate clinical benefit rate, defined as stable disease for  $\geq 12$  weeks complete or partial response using RECIST 1.1 guidelines in a similar manner. We will also perform similar analyses using Immune Related RECIST (irRECIST).

PFS is defined as the time from date of treatment initiation until date of documented disease progression or death (by any cause in the absence of progression). OS is defined as the time from the date of start of treatment until death due to any cause. For patients alive at the time of data cut-off, PFS and OS will be censored as of the last tumor assessment date or known to be alive, respectively. The PFS and OS will be estimated using the Kaplan-Meier method. The number, frequency, and severity of adverse events (as defined by the NCI Common Terminology Criteria for Adverse Events or CTCAE version 4.03) will be recorded.

Baseline percent PDL1 expression, TILs (sTILs, iTILs, and their ratio), and changes in T cell subpopulations will be used as a continuous variable to predict clinical benefit or overall response rates using appropriate statistical summaries. Cox proportional hazards regression will be used to compare how these biomarkers are associated with PFS and OS as well.

Changes from baseline in these biomarkers will also be analyzed to assess for pharmacodynamic effects of treatment. Continuous variables will be analyzed using either paired t-tests, signed rank tests or repeated measures analysis of variance.

For analysis of each T cell receptor clonotype, we will apply a newly-developed algorithm Bowtie2 aligner (Ref; Nature methods 2012; 9:357-9), in collaboration with Profs. [name] and [name] in Human Genome Center, The University of Tokyo. We will assign each of V, (D), J and C segments in the TCRA and TCRB reference sequences provided by IMGT/GENE-DB (Ref; Nucleic acids research 2005; 33:D256-61). By our approach, we will also identify novel exons that are not deposited in the reference sequence database. After decomposition of T cell receptor sequencing reads into V, (D), J and C segments, we will determine amino acid sequences of CDR3 (complementarity determining region 3), which plays a critical role in recognition of antigen. We will also calculate the diversity index (inverse Simpson's index) in CDR3 sequences to assess overall diversity and clonality in the T cell receptor clonotypes. Descriptive statistics will be used to assess differences from baseline to two months, and their relationship with clinical endpoints.

Determination of response rate to subsequent next line therapy will be determined in a similar manner as to the primary objective when feasible, where ORR is defined as number (%) of patients with at least one visit response of PR or CR. In instances where data for this post-hoc analysis cannot be obtained and only clinical responses can be obtained (ie patient followed up at an outside institution and only clinical radiograph reports are available), these will be used. Best objective response prior to disease progression will be used. Response rates will be calculated using proportions and the 80% and 95% confidence intervals will be estimated using the exact binomial distribution. Duration of response to next line therapy will be defined as date from next line therapy until date of last dose of next line therapy. The Kaplan-Meier method will be used to assess duration of response to next line therapy.

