## **STUDY SUMMARY**

**NU Study Number: NU 15B01**  
**Other Study Number: MedImmune # ESR-14-10694 (D4190C00030)**

Title	A Single Arm Phase II Study Evaluating the Efficacy and Safety of Durvalumab (MEDI4736) In Combination With Tremelimumab In Patients with Metastatic HER2 Negative Breast Cancer: TNBC expansion cohort
Short Title	Durvalumab and Tremelimumab in Metastatic Breast Cancer
Version	Amendment 12 dated 8.31.2020
Study Design	Phase II
Study Center	Northwestern University
Objectives	
Primary Objective:  To evaluate overall response rate (ORR) in patients with metastatic HER2 negative breast cancer treated with durvalumab in combination with tremelimumab.
 
Expansion Cohort Objective: To evaluate overall response rate (ORR) in patients with metastatic triple negative breast cancer treated with durvalumab in combination with tremelimumab.
 
Secondary Objectives:  To evaluate PFS and OS in patients with metastatic HER2 negative breast cancer treated with durvalumab in combination with tremelimumab.  To evaluate clinical benefit rate in this population.  To evaluate safety and tolerability.
 
Exploratory:  To evaluate if serum and tissue-based immune-related biomarkers are modulated by therapy and predict response. (see Section 2.3 for details)  To assess response rates to next line therapy after progression

Sample Size	A total of 30 patients (15 ER+, 15 ER-) with metastatic breast cancer which is HER2 negative will be enrolled into this study and receive durvalumab in combination with tremelimumab in order to get 28 evaluable (14 ER+, 14 ER-) for response. Expansion cohort based will enroll 20 additional patients with TNBC to determine the posterior Bayesian probability that the response rate exceeds 30%.

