### **10.0 STATISTICAL CONSIDERATIONS**

#### **10.1 Study Design/Study Endpoints**

This will be a single-arm, open-label, pilot phase II study to assess the efficacy and safety of durvalumab in combination with tremelimumab in patients with stage IV breast cancer which is HER2 negative. Patients who have completed the week 16 CT or nuclear bone scan will be evaluable for response endpoints. (*Note: Bone scans will be done only if the patient has bone disease. PET-CT is acceptable in place of bone scan, if a bone scan is contra-indicated for a patient's disease. The same modality used at baseline should be used throughout.*)

The **primary endpoint** is ORR, defined as number (%) of patients with at least one visit response of partial response (PR) plus complete response (CR) in patients with metastatic HER2 negative breast cancer treated with durvalumab in combination with tremelimumab using the Response Evaluation Criteria in Solid Tumors (RECIST) Version 1.1 (23). Any patient who has completed two months of study therapy is evaluable for this end point.

**Secondary endpoints** include PFS and OS, where PFS is defined as the time from date of treatment initiation until date of documented disease progression or death (by any cause in the absence of progression), and OS is defined as the time from date of treatment initiation until death due to any cause. Clinical benefit rate (SD for  $\geq$  12 weeks + PR + CR) will be assessed. Any patient who has completed two months of study therapy is evaluable for this end point.

The safety endpoints will be the number, frequency, and severity of adverse events (as defined by the NCI Common Terminology Criteria for Adverse Events or CTCAE version 4.03) will be recorded. Any patient treated with minimum 1 dose of either study drug will be evaluable for toxicity.

The expansion cohort will follow a similar design but only include patients with metastatic TNBC. Responses will be captured by RECIST v1.1.

**Exploratory endpoints** include serum and tissue-based biomarkers including: circulating tumor DNA, immunohistochemical expression of PD-L1; TILs; changes in tissue and peripheral T cell receptor sequencing, mutational and neoantigen burden, and immune-related candidate gene signatures at baseline.

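### Section 10.3 calls a response-evaluable set ITT, its evaluability rules conflict, and Section 4.9 takes patients out of PFS and OS against the endpoint definitions

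*Combined protocol and SAP*

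**What the plan says.** **Primary population (10.3).** "The primary analysis will be on the intent-to-treat (ITT) population, including all evaluable patients".

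**Who is evaluable for response.**
- 10.1, opening paragraph: "Patients who have completed the week 16 CT or nuclear bone scan will be evaluable for response endpoints".
- 10.1, primary endpoint: "Any patient who has completed two months of study therapy is evaluable for this end point". No scan is named.
- 10.2: "Patients who have completed the week 8 CT or nuclear bone scan will be evaluable for response endpoints".
- 6.2: evaluable patients must have had two cycles and the 2-month scans.
- 4.9: a patient who does not reach the 2-month imaging is left out of ORR unless the reason is clinical progression. Further patients may be enrolled so that response can be assessed.

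**PFS and OS.** Section 4.9 applies the same exclusion to PFS and OS but keeps these patients in the safety analysis. Sections 2.2.1, 6.3 and 10.3 start both endpoints at treatment initiation and count death from any cause. Section 4.8 generally follows patients who stop treatment for progression and survival, with exceptions.

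**Planned numbers.** The Study Summary says: "A total of 30 patients (15 ER+, 15 ER-) with metastatic breast cancer which is HER2 negative will be enrolled into this study". Section 10.2 says: "A total of 35 patients (as needed) with metastatic breast cancer which is HER2 negative will be enrolled into this study". Both aim at 28 evaluable patients.

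**The concern.** A reader takes an ITT response rate to have every enrolled or treated patient in the denominator. Here a treated patient without a post-baseline scan cannot be recorded as a responder and can also leave the denominator.

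The edge of the evaluable set is unclear as well. An early clinical progressor without a scan is a certain non-responder, counted under 4.9 and not under 6.2. A patient who leaves after week 8 and before week 16 is evaluable under 10.2 but does not meet the week-16 sentence in 10.1. Two competent analysts could report different primary denominators.

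For PFS and OS the conflict is direct. A treated patient who dies before the 2-month scan without clinical progression has an event under the endpoint definitions and is absent under 4.9. At stake are the headline ORR and unbiased secondary survival estimates.

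**Working it through.** **1. The plan's own figures.** Inputs from 10.2: 11 patients in stage 1, continue with at least 2 responses, 27 in total, success with at least 6, null 10%, alternative 30%. (Section 3.0 gives a different stage plan; I use 10.2 because the error rates are stated for it.) With X1 ~ Bin(11, p) and X2 ~ Bin(16, p):

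P(pass) = sum over x1 ≥ 2 of P(X1 = x1) × P(X2 ≥ 6 − x1)

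| True rate in evaluable patients | Stop at stage 1 | Pass |
|---|---|---|
| 10% | 0.697 (stated 70%) | 0.0395 (stated 4%) |
| 30% | 0.113 | 0.806 (stated 80%) |

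Expansion cohort: a Beta(0.3, 0.7) prior with 8 of 20 gives Beta(8.3, 12.7), and P(rate > 30%) = 0.812 (stated 0.81). All stated figures reproduce on the evaluable denominator.

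**2. The evaluability rules side by side.** A cycle is 28 days (4.2), so two cycles, two months of therapy and the week-8 scan mark about the same visit. They differ only in edge cases, such as two months of therapy without a scan. Two conflicts remain:
- *Week 16 against week 8.* Section 10.1 also contradicts itself by accepting two months of therapy. The Amendment 6 entry in Appendix E records the same change, week 16 to week 8, in 10.2 as an error correction, so the sentence still in 10.1 looks like a remnant. Its effect has no fixed direction: it could drop patients who progressed at week 8, or a week-8 responder without a week-16 scan.
- *Early clinical progression without a scan.* Kept by implication in 4.9, excluded by 6.2.

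**3. ORR.** Take 6 responders and add treated, unscanned patients to the 27:

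| Added | ORR |
|---|---|
| 0 | 6/27 = 22.2% |
| 1 | 6/28 = 21.4% |
| 2 | 6/29 = 20.7% |
| 3 | 6/30 = 20.0% |

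**4. Chance of passing, upper-bound scenario.** Assume that the true all-treated rate is 10% and that the whole general-cohort allowance (30 or 35 enrolled for 28 evaluable) is treated but never scanned. The rate among evaluable patients is 0.10 divided by the evaluable fraction:
- 28/30: 0.10/0.933 = 0.107, P(pass) = 5.2%
- 28/35: 0.10/0.80 = 0.125, P(pass) = 9.5%

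**5. PFS and OS.** If a share d of treated patients dies before week 8 and is removed, with no earlier censoring, every later Kaplan-Meier value becomes S/(1 − d):
- one of 30: 0.500 × 30/29 = 51.7%
- two of 30: 0.500 × 30/28 = 53.6%

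Section 4.9 removes the whole patient, so later events go too. Suppose a patient stops early, misses the scan and dies at week 20. If 15 of 30 are alive after that, the curve reads 15/29 = 51.7%. If the removed patient is instead one of the 15 survivors, it reads 14/29 = 48.3%. The net direction therefore depends on who is removed.

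**The case against.** Much of the case on the other side stands.

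- *The rules mostly agree.* Only 6.2 says that scans are a must. The sentences in 10.1 and 10.2 can be read as sufficient conditions, and most of the rules point to the same visit. That is right, and it narrows the conflict to the two items in step 2.
- *The figures do not measure the rule conflict.* Steps 3 and 4 compare evaluable with all treated patients, a gap that any evaluable rule would leave. They show what the ITT label hides, not the cost of week 16 against week 8.
- *The number left out is not lost.* These patients stay in the safety analysis, and one dose of either drug makes a patient evaluable for toxicity, so safety N minus evaluable N largely recovers it.
- *The study is a closed single-arm pilot.* PFS and OS carry no test, and the estimates move by little per patient. This limits the severity.

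Three stronger readings are tempting, and the documents do not support them. A reader might infer that the type I error is really up to 9.5%. That needs a 10% null among all treated patients and the entire allowance unscanned, whereas 35 is qualified as needed and patients who leave before the first dose may also be replaced. A reader might infer that removal under 4.9 always flatters PFS and OS; step 5 shows otherwise. A reader might extend the allowance to the expansion cohort and discount its 0.81. The documents plan no overage there: "Expansion cohort based will enroll 20 additional patients with TNBC" in the Study Summary, and "The expansion cohort will include 20 evaluable patients with TNBC" in 3.0.

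**Conclusion.** The text is wrong as written and should be fixed; it does not invalidate the design. The primary set is response-evaluable, not ITT. The week-16 sentence in 10.1 conflicts with the rest, and 4.9 and 6.2 disagree on early clinical progressors. The PFS and OS exclusion in 4.9 contradicts the definitions in 2.2.1, 6.3 and 10.3.

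The gap between evaluable and all-treated ORR can only favour the treatment: about 2 percentage points (22.2% against 20.0%) if three treated patients are unscanned and there are 6 responders. This rests on unscanned patients being non-responders, which follows from the response criteria. The pass probability of 5.2% to 9.5% is an upper-bound scenario and not an estimate. Each removed early death among 30 treated patients lifts a 50% survival value by just under 2 points, but the net bias in PFS and OS has no fixed sign. All of these effects are zero if nobody is excluded.

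**What to change.** 1. Delete the week-16 sentence in 10.1.
2. Use one week-8 evaluable definition in 4.9, 6.2, 10.1 and 10.2, with early clinical progression or death without a scan counted as non-response.
3. Relabel the 10.3 population as response-evaluable.
4. Keep the cutoff of 6 at 27 evaluable patients. Carrying it to larger numbers at a 10% rate raises the pass probability to 5.7% at 30 and 9.0% at 35.
5. Delete the PFS and OS exclusion in 4.9. Analyse both endpoints in all patients with at least one dose, count every observed death, and censor patients whose observation ends under 4.8 at the last tumour assessment (PFS) or the date last known alive (OS).
6. Add a sensitivity ORR in all treated patients, with unscanned patients as non-responders and exact 80% and 95% intervals. Report how many were excluded and why.
7. Disclose that the harmonised definition, the PFS and OS population and the all-treated ORR were all set after general-cohort results were known (1.7.3) and after accrual closed (Appendix E, Amendment 12). Show the general-cohort result under the 6.2 definition as well.

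The cost is wording in five sections and a small added analysis, with no new data collection. Estimates may become slightly less favourable.
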